## 4 Study design

- Randomized, controlled, 2x2 crossover, phase III, non-inferiority clinical trial to evaluate the efficacy and safety of Nifedipine 30mg extended release Richmond via oral administration VS. Comparator via oral administration, in patients with primary hypertension, at a referral clinic in the city of Bogotá.

[figure not shown]
Target population: Patients with hypertension with normal blood pressure readings (SBP < 140 mmHg or DBP < 90 mmHg)

Source of subjects: Subjects participating in the study will be selected in doctors' offices, medication delivery points, and the community at large. After explaining the study to be conducted, its risks and benefits, verifying the inclusion and exclusion criteria, performing a medical evaluation, reviewing the results of screening studies, and obtaining informed consent.

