## 6.2 Treatment allocation method

Randomization/treatment assignment will be performed in permuted blocks at the research center by a person assigned and qualified for this activity who is not involved in the clinical evaluation of the participant, according to the following procedure (Figure 1):

- **Group A:** 8 weeks of treatment with Nifedipine Richmond New Formulation —  
-- 8 weeks of treatment with reference product (the first 2 weeks will be included for statistical silence).
- **Group B:** 8 weeks of treatment with reference product-----8 weeks of treatment with Nifedipine Richmond (the first 2 weeks will be included for statistical silence).

The random assignment method is by permuted blocks, where the random sequence will be taken between study groups A and B. The sequence will be carried out taking into account permutations 1. AB and 2. BA.

The random selection will use the random function (RANDOM: uniform distribution between 0 and 1) and the randomly selected sequence will be obtained using the equation  $\text{RANDOM} \times 2 + 1$ , taking the integer part; in the EXCEL Office 365 program.

**Table 2.** Random sequence list

Patient	Random	Randomx2+1	Sequence selected	Assigned sequence
1	0.67511186	2.350223724	2	BA
2	0.63655793	2.273115864	2	BA
3	0.82005771	2.640115417	2	BA

Product: 910002

4	0.75238537	2.504770731	2	BA
5	0.27060773	1.541215464	1	AB
6	0.13509461	1.27018922	1	AB
7	0.0059008	1.011801603	1	AB
8	0.00522046	1.01044092	1	AB
9	0.57459303	2.149186066	2	BA
10	0.13413163	1.268263257	1	AB
11	0.46855475	1.937109506	1	AB
12	0.43792582	1.875851646	1	AB
13	0.92905912	2.858118233	2	BA
14	0.76263057	2.525261134	2	BA
15	0.59039799	2.180795977	2	BA
16	0.67106409	2.342128183	2	BA
17	0.57513717	2.150274349	2	BA
18	0.95687127	2.91374253	2	BA
19	0.87915414	2.758308274	2	BA
20	0.51677593	2.033551866	2	BA
21	0.37768148	1.755362968	1	AB
22	0.13192216	1.263844313	1	AB
23	0.42201985	1.84403969	1	AB
24	0.20962522	1.419250439	1	AB
25	0.20456967	1.409139347	1	AB
26	0.65660156	2.313203122	2	BA
27	0.54821573	2.096431466	2	BA
28	0.91311981	2.826239619	2	BA
29	0.09187709	1.183754176	1	AB
30	0.66954146	2.339082914	2	BA
31	0.56996805	2.139936106	2	BA
32	0.35135826	1.702716511	1	AB
33	0.31718197	1.634363941	1	AB
34	0.42369607	1.84739214	1	AB
35	0.82200106	2.644002116	2	BA
36	0.50705857	2.014117148	2	BA
37	0.05075322	1.101506442	1	AB
38	0.03452872	1.069057445	1	AB
39	0.5778017	2.155603408	2	BA
40	0.74539157	2.490783148	2	BA

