#### 9.1 Summary of statistical analysis plan

Product: 910002

Design	Phase III, randomized, active-controlled clinical trial to evaluate the efficacy and safety of Nifedipine 30 mg extended-release in adult patients diagnosed with mild or moderate hypertension in Colombia.
Randomization	Permuted blocks, 1:1 ratio
Blinding	Double-blind
Analysis population	Efficacy assessment: Intention-to-treat (ITT) analysis Safety assessment: Analysis of patients treated (ASaT)
Criteria for Primary	Criteria
Secondary of assessment	Proportion of patients achieving the blood pressure control target (<140/90 mmHg) at week 4 of follow-up.  Proportion of patients experiencing serious and non-serious adverse events at week 8 of follow-up.
Statistical methods for efficacy analysis	Difference in mean SBP and DBP from baseline to weeks 4 and 8  Significance value and 95% CI for difference in mean SBP and DBP from baseline to 4 and 8 weeks between the two treatments (repeated measures ANOVA).  p-value or significance value and 95% CI for differences between the proportions of normal blood pressure readings (<140/90 mmHg) at 4 and 8 weeks between treatments using McNemar's chi-square test for differences in proportions with and without continuity correction or Fisher's exact test for paired designs (expected values < 5).
Statistical methods for safety analysis	Percentage of serious and non-serious adverse events between treatments and percentage by type of adverse event for each treatment (descriptive).
Size and power of the sample	A sample size of 50 patients is defined, each patient = 2 study subjects.

Product: 910002

For a maximum change of 3 mmHg between the two treatments, with 90% power, 95% reliability, and 10% losses, a 1:1 ratio, and a sample size of 50:50 (1 patient = 2 study subjects).

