## 9.3 Endpoints for analysis

### 9.3.1 Efficacy evaluation criteria

The primary efficacy endpoint will be the proportion of participants who achieve blood pressure control, i.e., below the threshold of 140/90 mmHg at week 8 of follow-up.

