### 9.5 Statistical methods

#### 9.5.1 Statistical methods for efficacy analysis

##### 9.5.1.1 Primary efficacy analysis

The difference in means and **95% CI** for **SBP and DBP** between the two treatments will be evaluated before and after the intervention at 4 and 8 months, using a fixed-effects repeated measures ANOVA and a Grizzle mixed linear model ANOVA for two crossover periods to adjust for possible carryover effects. The normality of SBP and DBP will be evaluated beforehand at baseline and at 4 and 8 weeks using the Shapiro-Wilk normality test.

The differences in the proportions of subjects with normal blood pressure readings (SBP < 140 or DBP < 90) at 4 and 8 weeks will be evaluated using McNemar's chi-square test for differences in proportions with and without continuity correction or Fisher's exact test for paired designs (expected values < 5).

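### The primary proportion is compared by McNemar's test, which ignores period; with the printed 22:28 sequence split, 12% of any period effect enters the estimated treatment difference

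*Protocol*

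**What the plan says.** Section 4 describes a "Randomized, controlled, 2x2 crossover, phase III, non-inferiority clinical trial". Section 9.3.1 fixes the main outcome: "The primary efficacy endpoint will be the proportion of participants who achieve blood pressure control", at week 8.

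For that proportion, section 9.5.1.1 specifies a comparison "using McNemar's chi-square test for differences in proportions with and without continuity correction", with a Fisher's exact test for paired designs when expected values fall below 5. Section 9.1 repeats the choice, "between treatments using McNemar's chi-square test for differences in proportions with and without continuity correction", and promises a 95% CI for the difference. Neither place mentions period or sequence.

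Mean systolic and diastolic pressure are treated differently. Section 9.5.1.1 gives them a repeated-measures ANOVA and "a Grizzle mixed linear model ANOVA for two crossover periods to adjust for possible carryover effects".

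On allocation, section 6.2 says "The random assignment method is by permuted blocks", and section 9.1 adds a 1:1 ratio. The list itself, Table 2, is built from one independent uniform draw per patient, which does not force balance.

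**The concern.** In a 2x2 crossover each patient's treatment contrast is also a contrast between periods. McNemar's test pools the discordant pairs over both sequences, so a general change in control between the periods cancels only when as many patients take Richmond first as take it second. The printed list does not have that balance.

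Some change between periods is conceivable. Therapeutic education, daily home measurement and reminders run through the whole study. The protocol recognises the two-period structure for the means but not for the endpoint it calls primary. At stake is a shift in the estimated difference in control, and in the centre of its confidence interval, that has nothing to do with the products. In a non-inferiority trial the direction of such a shift matters.

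**Working it through.** **Plan's own figure.** The sample size reproduces. With one-sided 2.5% significance, 90% power, a 3 mmHg margin and an SD of 6 mmHg, the normal approximation gives ((1.960 + 1.282) × 6/3)² = 42.03, so 43 pairs. The paired t calculation gives 44 pairs (power 0.900), as stated. It concerns mean blood pressure and does not bear on the test for the proportion.

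**Inputs**
- Sequences, counted from all 50 rows of Table 2: 22 AB and 28 BA. Recomputing the integer part of RANDOM × 2 + 1 matches every printed label.
- Period effect on the proportion controlled: not in the protocol. Assumed range: 2 to 20 percentage points.
- Reading of AB: Richmond first, inferred from Groups A and B in section 6.2.

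**Leakage.** Let d be the proportion controlled in period 1 minus that in period 2, with no true treatment difference and no carryover. The expected Richmond-minus-comparator difference is +d in AB and −d in BA. Pooled over patients:

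(22 × d − 28 × d)/50 = −0.12 d

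| Assumed period effect (points) | Size of bias (points) |
|---|---|
| 2 | 0.24 |
| 5 | 0.6 |
| 10 | 1.2 |
| 15 | 1.8 |
| 20 | 2.4 |

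If control worsens (d > 0), the bias is against Richmond. If control improves (d < 0), it favours Richmond.

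**Simulation checks, no treatment effect**
- Latent correlation 0.6, 40,000 runs, split 22:28. Control of 90% then 80% gives a pooled difference of −1.15 points (SE 5.84) and an equally weighted difference of +0.05 (SE 5.89). Control of 85% then 70% gives −1.81 and −0.02.
- Latent correlation 0.5, 20,000 runs. Control of 85% then 75% gives −1.21 points at 22:28 and −0.08 at 25:25. Control of 85% then 65% gives −2.38 and +0.06.
- In the second set, uncorrected McNemar rejected equality at the two-sided 5% level in about 4.2% of runs for both scenarios at 22:28.

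All these runs model worsening control. Exchanging the two periods' control rates reverses the sign of the bias. Relative to sampling error, the bias at 10 points is 1.15/5.84 = 0.20 SE.

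**Effect of losses.** Section 4.2.1 sizes the trial at 44 pairs out of 50 patients. If all six lost pairs came from AB, the split would be 16:28 and the leakage 12/44 = 27%. If all came from BA, it would be 22:22 with no leakage.

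**Price of adjustment.** Weighting the sequences equally gives ½[(+d) + (−d)] = 0 leakage for any split. With equal within-sequence variances, the variance ratio to the pooled estimate is

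¼ × (1/22 + 1/28) ÷ (1/50) = 1.015,

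so the SE rises by √1.015 − 1, about 0.7%.

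**The case against.** The strongest reply is that the effect is small and depends on a period effect nobody has documented. Patients enter already controlled for four weeks, already taking nifedipine, with dose and combination held fixed, so a large change between periods is not obvious. The sized comparison, with its 3 mmHg margin, is on means and does get a two-period model. No margin is stated for the proportion, so no conclusion can be shown to change. The imbalance also comes from the list: at 25:25 the expected leakage under McNemar would be zero. All of this stands and limits the weight of the point. It does not remove it, because the printed list is 22:28, later losses can unbalance any list, and the section that names the primary test leaves period out.

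Fisher's exact test for paired designs could be meant as a sequence-by-preference test, which would handle period. The text does not say so and offers it only for small expected counts.

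A reader might infer more than the protocol supports:
- **That the analysis favours Richmond.** This needs improving control and AB meaning Richmond first. Section 6.2 uses A and B for whole treatment groups, and the synopsis puts Richmond first in both groups, so the reading is likely but not stated. From starting control of 85 to 90%, an improvement of 15 points is barely possible or impossible.
- **That false-positive rates are inflated.** The simulated test of equality stayed below 5%. That is not the non-inferiority decision, for which a favourable shift of 0.2 SE would raise a one-sided 2.5% error to 1 − Φ(1.96 − 0.20), about 4%. But this needs a 10-point improvement.
- **That dropout makes it worse.** Losses can enlarge or reduce the imbalance, as the 16:28 and 22:22 cases show.
- **That period 2 is longer.** The synopsis and schedule imply 10 weeks of treatment before the final reading, against 8 in period 1. Section 6.2 gives 8 weeks including the silent weeks. These passages must be reconciled before the difference in exposure can be used as an argument.

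**Conclusion.** The point holds as a modest, avoidable bias in the primary comparison. The test for the primary proportion omits period, and with the printed list 12% of any period effect passes into the estimated difference. The 12% follows by arithmetic from Table 2 and applies if the analysed patients keep the 22:28 split. The size in percentage points, 0.24 to 2.4, rests on an assumed period effect of 2 to 20 points. The direction depends on whether control improves or worsens and on AB meaning Richmond first. The protocol does not establish that the result will favour either product. The change is worth making because it is cheap and removes dependence on the final split, not because the trial's conclusion is shown to be at risk.

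**What to change.** In sections 9.1 and 9.5.1.1, make the primary comparison of proportions period-adjusted. Estimate the difference as

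½ × (mean Richmond-minus-comparator difference in AB + the same mean in BA),

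with variance ¼ × (s²_AB/n_AB + s²_BA/n_BA) and a 95% CI. A Mainland-Gart or Prescott test, or a GEE or conditional logistic model with treatment and period, would also serve. Keep McNemar as a sensitivity analysis, and state which product is taken first under AB and under BA.

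The mismatch between permuted blocks at 1:1 and independent draws in Table 2 should be reconciled as well. A balanced list alone would not protect against unequal losses, so the analysis change is needed either way.

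The cost is analysis wording only, made before unblinding: no extra patients, visits or data, about 1.5% more variance, and under 1% on the standard error.

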##### 9.5.1.2 Secondary efficacy analysis

The percentage of serious and non-serious adverse events and the type of event will be measured for each treatment (descriptive).

#### Handling of missing data

Two types of missing data are defined:

- Intermittent losses (IL): resulting from missed visits that have no bearing on the primary efficacy endpoint.
- Monotonic losses (ML): due to early withdrawal of the participant.

The analysis of missing data to be used as the main method will be Observed Failure (in the case of IL, the data will be excluded; in the case of ML, it will be considered without failure). The method of identifying failure as a participant who did not complete follow-up will be used as a backup method for secondary analysis.

#### 9.5.2 Statistical methods for safety analysis

Safety will be evaluated using inferential analysis to determine the statistical significance of comparisons between treatment groups, indicating p-values and 95% CIs for the evaluation of the proportion of patients who experienced an AE or SAE related or unrelated to the study drug.

Product: 910002

### 9.5.3 Summaries of baseline characteristics, demographics, and other analyses

Relevant characteristics will be evaluated by treatment group using descriptive statistics, presenting the number and percentage of participants.

The selected, randomized population and the main reasons for non-compliance for selection and reasons for discontinuation/withdrawal will be indicated.

Demographic variables such as age and sex, baseline characteristics, previous and concomitant treatments will be summarized using descriptive statistics for continuous or categorical variables, as appropriate.

### 9.6 Sample size calculation and sample power

The primary endpoint is defined as a maximum change of 3 mmHg between the two treatments, with a power of 90%, reliability of 95%, and losses of 10%, a 1:1 ratio, and a sample size of 50:50 (1 patient = 2 study subjects).

### 9.7 Subgroup analysis

To determine whether the treatment effect is consistent across different subgroups, the treatment effect estimate between groups for the primary efficacy endpoint will be analyzed according to:

- Age category ( $\leq 60$  vs.  $> 60$  years)
- Gender (female, male)

Other clinically important variables may be identified for which other subgroup analyses may be performed. If the subgroup category contains fewer than 15 participants in any of the treatment groups, only descriptive statistics will be presented.

### 9.8 Compliance (Compliance with medication administration)

Compliance will be defined for each participant as the ratio of the number of days on treatment (on which the participant actually took the dose as reported in the diary and verified by counting at the follow-up visit) to the number of days from randomization to the last scheduled day according to the study or the last day of medication intake in case of interruption.

Compliance rates will be presented for each treatment group in a descriptive manner.

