#### Sample size.

The sample size was estimated for the non-inferiority crossover study.

When comparing Richmond oral VS. oral comparator, in patients diagnosed with mild or moderate hypertension, who entered the study baseline with controlled blood pressure readings (SBP < 140 or DBP < 90 mmHg), where a maximum change of 3.0 mmHg was taken as the maximum level of change between the two treatments in SBP and DBP, for the hypothesis of non-inferiority in blood pressure control, to an alternative tail taking a 2.5% significance level with 90% power, with a standard deviation of the difference in means of 6 mmHg, the sample size is n=44 pairs (88 subjects in 44 patients) and with a 10% loss adjustment of 50 pairs (100 subjects in 50 patients), with a 1:1 ratio.

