## 9.4 Populations for analysis

### 9.4.1 Population for efficacy analysis

The total randomized population will be analyzed for the efficacy analysis (Intention-to-Treat-ITT). Additionally, a per-protocol (PP) analysis is proposed as a complementary analysis, in which the population is analyzed excluding participants with identified significant protocol deviations that could significantly affect the efficacy assessment, specifically, non-compliance in drug administration (non-adherence to treatment identified in follow-up visits by counting units and recording in a diary).

Product: 910002

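### The compliance ratio in section 9.8 scores early stoppers at 100% and spans both crossover products, and the per-protocol analysis is only complementary in a non-inferiority trial

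*Protocol*

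**What the plan says.** Section 9.8 defines compliance once per participant: days on which the dose was taken, divided by the days "from randomization to the last scheduled day according to the study or the last day of medication intake in case of interruption". It adds that "Compliance rates will be presented for each treatment group in a descriptive manner". It states no other use for the ratio.

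Section 9.4.1 makes the full randomized population (ITT) the basis of the efficacy analysis and says that "a per-protocol (PP) analysis is proposed as a complementary analysis". Participants are left out of it for deviations that could affect efficacy, "specifically, non-compliance in drug administration", identified from unit counts and the diary. It does not refer to section 9.8.

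The design in section 4 is a "Randomized, controlled, 2x2 crossover, phase III, non-inferiority clinical trial". The sample-size paragraph in section 4.2 sets the margin ("a maximum change of 3.0 mmHg was taken as the maximum level of change between the two treatments in SBP and DBP"), the error rate and power ("to an alternative tail taking a 2.5% significance level with 90% power") and the spread ("with a standard deviation of the difference in means of 6 mmHg").

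**The concern.** Two features of the formula give a misleading figure. In case of interruption the denominator ends at the last day of intake, so the days not taken after stopping disappear from both parts of the ratio. And because the clock starts at randomization and each participant has one ratio, in a crossover it averages over two different products. If treatment group in 9.8 means product, the ratio cannot supply the rates promised. If it means sequence, the rates can be tabulated but describe neither product.

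Adherence matters more here than in a superiority trial. When participants miss doses of both products, the contrast between the products shrinks, and in a non-inferiority comparison that favours the claim. A per-protocol analysis is the usual check. Under the plan it plays no part in the conclusion, and the only compliance measure the protocol defines would be a poor basis for it if it were used.

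**Working it through.** **Inputs.** Margin 3 mmHg, SD of the paired difference 6 mmHg, one-sided 2.5%, power 90%, 44 pairs, 50 patients after 10% loss (section 4.2). First period 8 weeks = 56 days. Second period 8 weeks = 56 days (section 6.2) or 10 weeks = 70 days (Synopsis, treatment groups; Appendix 6 also uses 18 weeks in total). The total is therefore 112 or 126 days.

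**The plan's own figure.** n = (6 × (1.960 + 1.282) / 3)² = 42.03, or 43 pairs by the normal approximation. The noncentral t gives 44 (power 0.900), which matches. Then 44/0.9 = 48.9, or 49 against the stated 50, which is close enough. The sample size is not affected by this point.

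**Early stopping.** All doses are taken up to the stop day.

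| Stop day | Ratio under 9.8 | Share of 126 days | Share of 112 days |
|---|---|---|---|
| 7 | 7/7 = 100% | 5.6% | 6.3% |
| 14 | 100% | 11.1% | 12.5% |
| 28 | 100% | 22.2% | 25.0% |
| 56 | 100% | 44.4% | 50.0% |

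Against the first period alone, a stop on day 7 is 7/56 = 12.5%.

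**Pooling of products.** Take full intake in period 1 and 60% in period 2.

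- 10-week second period: (56 + 0.6 × 70)/126 = 98/126 = 77.8%.
- 8-week second period: (56 + 0.6 × 56)/112 = 89.6/112 = 80.0%.

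A single figure of 78% to 80% stands for 100% on one product and 60% on the other.

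**Dilution, illustration only.** Assume that the true deficit is exactly 3 mmHg when both products are taken, and that a fraction f of participants contributes no difference because they take neither product properly. The mean difference is then 3(1 − f), and the chance of wrongly concluding non-inferiority is Φ(3f/(6/√n) − 1.960).

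| f | n = 44 | n = 50 |
|---|---|---|
| 0 | 2.5% | 2.5% |
| 10% | 5.2% | 5.4% |
| 20% | 9.7% | 10.5% |

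The noncentral t gives 5.1% and 9.5% at n = 44, and 5.3% and 10.3% at n = 50. The values of f are assumed.

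**The case against.** A reader might infer that the per-protocol set is built on the 9.8 ratio, so that early stoppers stay in it and non-adherence passes as non-inferiority. The documents do not support that chain.

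- Section 9.4.1 uses unit counts and the diary, names no ratio and does not point to 9.8. Section 9.8 gives its ratio a descriptive use only.
- A participant who stops but keeps attending returns unused units (section 6.5), so the count can reveal the stop.
- Adherence is checked at each follow-up visit (section 8.1; schedule of activities) and recorded by visit (Table 3). Visits 1 and 2 fall before the switch and visits 3 to 5 after it, so the data can show on which product doses were missed.
- Non-adherence need not favour non-inferiority. Doses missed only on the test product work against it; doses missed only on the comparator work for it. Someone who stops for good in period 1 has no second-product value and gives no within-patient mean difference to dilute.
- The dilution figures rest on an assumed fraction and on the mmHg scale, whereas section 9.3.1 makes the primary endpoint a proportion controlled.

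All of this stands. It is also true that ending the denominator at last intake is a recognised way to describe adherence while on treatment, that reasons for withdrawal are reported separately (section 9.5.3), and that a per-protocol compliance cut-off may properly be left to a statistical analysis plan. None of it repairs the formula: 9.8 offers its ratio as the participant's compliance for the study, and one ratio from randomization still cannot describe two products.

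**Conclusion.** The point holds in a limited form. The 9.8 formula is wrong for this design: it returns 100% for any fully adherent early stopper, where 5.6% to 50% of the planned days were taken for stops on days 7 to 56, and it merges the two products into one number. Any harm to the per-protocol set is conditional. If the ratio were used there, it would miss early stopping and hide product-specific non-adherence, but 9.4.1 does not say that it will be used.

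Separately, the protocol fixes the per-protocol analysis as complementary in a non-inferiority trial, where dilution from non-adherence on both products is a known hazard. How large that hazard is here cannot be said, because the documents give no non-adherence rate. The rise in error from 2.5% to about 5% to 10% shows sensitivity to an assumed 10% to 20% dilution and is not a forecast. The change is worth making but does not threaten the sample size.

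**What to change.** - **Section 9.8.** Compute compliance per participant and per period (hence per product) as days taken divided by days planned for that period, from the visit counts and diary already collected. Count early stopping against the plan. Say whether the two weeks of statistical silence belong to the planned days, and present rates by product.
- **Period length.** The Synopsis and section 6.2 must be reconciled on the second period (10 or 8 weeks) before planned days can be fixed.
- **Section 9.4.1.** Refer to this per-period measure when forming the per-protocol set, and state that non-inferiority is concluded only if the per-protocol confidence interval supports the ITT result.

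The cost is some wording, one extra derivation, a somewhat smaller per-protocol set and a slightly stricter decision rule. Under the plan's own assumptions and no true difference, power by the noncentral t is 90.0% with 44 pairs and 88.6% with 42, so losing two pairs from the per-protocol set costs about 1.4 percentage points in that analysis.
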